8.5 Costs, Subject Compensation, and Research Related Injuries

Subjects (or their parent/guardian) in Mali will be compensated for their time in this study and be reimbursed for travel to attend study visits. These will be explained in the ICF. Study subjects (or their parent/guardian) will not be charged for study immunizations, research clinic visits, research-related examinations, or research-related laboratory tests. As part of the assessment and management of AEs, all medical care required by the subjects according to good national medical practice will be provided by the study team for the study duration and the subject's parent/guardian will not need to pay for this. Subjects may be compensated for their participation in this trial. Compensation will be in accordance with the local IRB's policies and procedures, and subject to IRB approval.

If it is determined by the site principal investigator that an injury occurred to a subject as a direct result of the tests or treatments that are done for this trial, then referrals to appropriate health care facilities will be provided to the subject. Clinical trial insurance is legally required in Mali. Study personnel will try to reduce, control, and treat any complications from this trial, but chronic care will not be provided. Immediate medical treatment may be provided by the participating site.

9 STATISTICAL CONSIDERATIONS

9.1 Overview and Study Design

This is a Phase 3, randomized, single site, blinded non-inferiority trial to test the safety and immunogenicity of the NmCV-5 vaccine when administered at 9 months of age and when administered at 15 months of age. All participants will be randomly assigned to receive either NmCV-5 or MenACWY-TT, and all participants will be randomly assigned to receive one of these vaccines at either 9 months of age or at 15 months of age, along with scheduled EPI vaccines (Section 2.1).

9.2 Study Hypotheses

The co-primary objectives of the study are to demonstrate non-inferiority of the overall seroprotective response of NmCV-5 as compared to the seroprotective response of MenACWY-TT when administered as a single dose at either 9 months of age or 15 months of age. To achieve these co-primary objectives, the study will test the null hypothesis that the seroprotective response elicited by NmCV-5 to at least one of the meningococcal serotypes A, C, W, X or Y is inferior to the seroprotective response elicited by MenACWY-TT in favor of the alternative hypothesis that the seroprotective response to all five meningococcal serogroups elicited after one dose of NmCV-5 are non-inferior to those elicited by one dose of MenACWY-TT. For each vaccination age group and for each of the serogroups A, C, Y and W, the corresponding hypothesis test will be based on the difference in the proportion of participants randomized to receive NmCV-5 who show seroprotective response to the specific serogroup, relative to the proportion of participants randomized to receive MenACWY-TT who show seroprotective response to the same serogroup. For serogroup X, the hypothesis test will be based on the difference in the proportion of participants randomized to receive NmCV-5 who show seroprotective response to the serogroup X relative to the proportion of participants randomized to receive MenACWY-TT showing seroprotective response to the serogroup with the lowest proportion of seroprotective response in that arm. For each meningococcal serogroup, vaccine seroprotective response will be based on a rabbit serum bactericidal antibody (rSBA) assay and the primary immunological endpoint is defined as post-vaccination rSBA titers ≥ 8 at Day 29. Within each age group, non-inferiority of the vaccine for each serogroup will be declared if the lower bound of the two-sided 95% confidence intervals for the difference in proportions of participants with seroprotective response is above -10% (-0.1). Overall non-inferiority at a given vaccination age (at 9 months of age and at 15 months of age) will be declared if the criteria for non-inferiority of the vaccine seroprotective response, as defined above, is achieved for all five serogroups.

Consistent with the secondary safety endpoint to assess the safety and tolerability of a single dose of NmCV-5, a descriptive analysis approach will be used, with no statistical tests of hypothesis. These analyses are described in Section 9.6.

A secondary immunogenicity objective is to demonstrate the superiority of the NmCV-5 vaccine to elicit seroprotective response to the meningococcal serogroup X. To achieve this objective, the study will test a null hypothesis of the difference in the proportion of participants with vaccine seroprotective response to serogroup X equal or less than 30% (0.3) versus an alternative hypothesis of the difference in proportions of 30% or greater. Vaccine seroprotective response to serogroup X has been defined above, with non-inferiority declared if the lower bound of the two-sided 95% confidence interval for the difference in proportion of participants with seroprotective response is at or above 10%.

The secondary objective related to the immunogenicity of EPI vaccines is to demonstrate that seroprotective response elicited by EPI vaccines when co-administered with NmCV-5 is non-inferior to the seroprotective response elicited by these same vaccines when co-administered with MenACWY-TT. The study will test the null hypothesis that, for each EPI vaccine, the difference in the proportion of participants showing seroprotective response (in the NmCV-5 arm relative to the MenACWY-TT arm) is equal or less than 10% (-0.1) in favor of the alternative hypothesis that the difference is greater than -10% (0.1). The seroprotective response to measles vaccination is defined as anti-measles IgG concentration > 90 mIU/mL, the seroprotective response to yellow fever vaccine is defined as neutralizing antibody titers \geq 1:8, and the seroprotective response to rubella vaccine is to be according to the manufacturer's specified cutoff, for a commercially-available and validated rubella IgG assay, all from samples collected at Day 29 visit. For each EPI vaccine, non-inferiority will be declared if the lower bound of a two-sided 95% confidence interval of the difference in proportion of participants with seroprotective response is above -10% (-0.1).

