3 STUDY INTERVENTION/INVESTIGATIONAL PRODUCT

3.1 Study Product Description

3.1.1 Formulation, Packaging, and Labeling

NmCV-5 Vaccine: Active Product(s) and Components

The NmCV-5 investigational vaccine, manufactured by SIIPL, is formulated as a lyophilized powder containing meningococcal serogroups A and X polysaccharides conjugated to TT and meningococcal serogroups C, W and Y polysaccharides conjugated to CRM₁₉₇ protein. The vaccine is to be reconstituted with normal saline just prior to administration. The NmCV-5 lyophilized powder component contains sucrose, sodium citrate and trometamol as excipients. This vaccine is presented as a freeze-dried powder in a single-dose vial.

0.9% Sodium Chloride (normal saline) is the diluent used to prepare NmCV-5 and it is provided with vaccine. The diluent is a clear, colorless liquid. For the preparation of the NmCV-5 from a single dose vial, the contents are contemporaneously reconstituted with 0.63 ± 0.03 mL of provided diluent (normal saline). After reconstitution, a single 0.5 mL dose of NmCV-5 injectable solution will have the following composition: 5 mcg of weight for each of the five polysaccharides (A, C, Y, W, and X), tetanus toxoid, CRM₁₉₇, sucrose, sodium citrate, TRIS (trometamol), and sodium chloride.

MenACWY-TT: Comparator Vaccine

The comparator vaccine is the licensed meningococcal ACWY-TT conjugate vaccine, manufactured by Pfizer. MenACWY-TT is supplied as a single-dose vial of lyophilized powder containing meningococcal serogroups A, C, W, and Y polysaccharides conjugated to TT; the vaccine vial also contains sucrose and trometamol as excipients. The vaccine is to be reconstituted with the solvent, consisting of sodium chloride and water for injection, from a pre-filled single-use syringe. The reconstituted MenACWY-TT vaccine contains: 5 mcg of weight for each of the four polysaccharides (A, C, W, and Y), tetanus toxoid, sucrose, trometamol, and sodium chloride.

Measles and Rubella Vaccine

The MR vaccine is WHO-PQ and manufactured by SIIPL. MR is prepared from live, attenuated Edmonston-Zagreb measles virus and Wistar RA27/3 rubella virus propagated in human diploid cells. MR is supplied as a single-dose vial of lyophilized powder, when reconstituted with the provided diluent in the vaccine package, each dose of 0.5 mL contains ≥ 1000 CCID₅₀ (cell culture infective dose 50%) measles virus and ≥ 1000 CCID₅₀ rubella virus.

Yellow Fever Vaccine

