8 HUMAN SUBJECTS PROTECTION

8.1 Institutional Review Board/Independent Ethics Committee

This study will be conducted in accordance with the ethical principles set out in the World Medical Association Declaration of Helsinki, The Council for International Organizations of Medical Sciences (CIOMS) International Ethical Guidelines for Biomedical Research Involving Human Subjects, and in conformity with ICH GCP and with local Mali applicable regulations.

This study will be conducted under the auspices of the following Institutional Review Boards (IRBs)/ Ethics Committees (ECs):

- Research Ethics Committee of the Faculté de Médecine, de et d’Odonto-Stomatologie – Faculté de Pharmacie (FMOS-FAPH), Bamako, Mali (DHHS OHRP Federal Wide Assurance number 00009970)
- University of Maryland, Baltimore Institutional Review Board (UMB IRB), Baltimore, Maryland, U.S.A. (DHHS OHRP Federal Wide Assurance number 00007145)

The principal investigator will obtain EC/IRB approvals for this protocol and send supporting documentation to the DMID before initiating recruitment of subjects. The IRB/IEC must be registered with OHRP as applicable to the research. DMID must receive the documentation that verifies IRB/IEC-approval for this protocol, associated informed consent documents, and upon request any recruitment material and handouts or surveys intended for the subjects, prior to the recruitment and enrollment of subjects. Any amendments to the protocol or consent materials will be approved by the IRB/IEC before they are implemented. IRB/IEC review and approval will occur at least annually throughout the enrollment and follow-up of subjects and may cease if annual review is no longer required by applicable regulations and the IRB/IEC. The investigator will notify the IRB/IEC of deviations from the protocol and reportable SAEs, as applicable to the IRB/IEC policy.

The IRB/IEC will determine that adequate provisions are made for soliciting the permission of each child's parent(s) or legal guardian, including whether permission of one parent is sufficient for research or whether permission is to be obtained from both parents.

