Analysis of the Secondary Immunogenicity Endpoint(s)

The superiority of seroprotective response to serogroup X among those randomized to NmCV-5 relative to those randomized to MenACWY-TT will be based on the difference in proportions of participants with seroprotective response to serogroup X and its 95% CI, as estimated using the Miettinen-Nurminen method.

The non-inferiority of seroprotective response to EPI vaccines administered concurrently with the NmCV-5 or MenACWY-TT meningococcal vaccines will be based on the difference in the proportion of participants with seroprotective response to each of these vaccines, between vaccination arms. The difference of proportions and the corresponding 95% CI will be calculated using the Miettinen-Nurminen method.

Finally, to better understand and illustrate the immunological response elicited by the NmCV-5 and MenACWY-TT vaccines, further descriptive analyses will be conducted by vaccination arms for each of the vaccination schedules. These include estimating the proportion of participants (along with 95% confidence intervals) with rSBA titers above 32 and above 128 at their Day 29 visit, as well as the proportion of participants with a 4-fold increase from baseline to their Day 29 visit. Geometric Mean Titers (GMT), with 95% CIs, will also be reported. Similar descriptive analyses will be done at other timepoints (at Day 181 and Day 730 visits), to explore the duration of the immunological response.

Analysis of the Safety Secondary Endpoint(s)

Analysis of the secondary safety endpoint, as well as descriptive analyses of safety data (solicited signs and symptoms and AEs) will be presented for the Safety Analysis Population.

Solicited reactogenicity signs and symptoms (local and systemic) will be summarized by severity for each day post vaccination (Days 1-8) and as the maximum severity over all 7 days. The number and proportion of participants reporting each of the solicited reactogenicity signs and symptoms will be reported, along with 95% confidence intervals, as well as the number and proportion of participants reporting (i) any solicited reactogenicity sign or symptom, (ii) any solicited local reactogenicity sign or symptom and (iii) any solicited systemic reactogenicity sign or symptom.

Unsolicited non-serious AEs will be collected from the time of first vaccination through 28 days after each vaccination. Unsolicited AEs will be coded by the Medical Dictionary for Regulatory

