## 3.2 Analysis Sets

Unless otherwise specified, each of the following definitions refers to two analysis sets: one for Group 1 (participants randomized in Step 1 to receive the study meningococcal vaccine at 9-11 months of age) and one for Group 2 (participants randomized in Step 1 to receive the study meningococcal vaccine at 15-17 months of age).

In cases where an analysis set has also been defined in Section 9 of the Protocol, the definition provided here will supersede that of the protocol.

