**Endpoints:**

- Seroprotective response to serogroup X in the NmCV-5 arm at Day 29,
- seroprotective response to serogroup X MenACWY-TT arm at Day 29,

with seroprotective response is defined as rSBA antibody titers  $\geq 8$ .

**Strata:** Age group (from Step 2 randomization): Group 1 (9-12 months) and Group 2 (15-18 months of age).

**Analysis Set(s):** The primary analysis will be conducted on the Per Protocol (PP) Analysis Set, with a secondary analysis conducted on the Meningitis mITT Analysis Set.

**Approach:** The proportion of infants (randomized to NmCV-5 vs. MenACWY-TT) with a seroprotective response to serogroup X will be calculated as

$$p_{V,X} = \frac{\sum_{i=1}^{N_V} I(Y_i^{V,X} \geq 8)}{N_V} = \frac{n_{V,X}}{N_V},$$

where V indicates arm (NmCV-5 vs. MenACWY-TT), X indicates serogroup X,  $N_V$  is the number of infants in the analysis set randomized to arm V and  $Y_i^{V,X}$  is the rSBA antibody titer to serogroup X for the  $i^{\text{th}}$  infant in arm V.

NmCV-5 will be deemed superior to MenACWY-TT for eliciting a seroprotective response to serogroup X, by at least 30%, if the lower limit of the 95% confidence interval for  $p_{NmCV-5,X} - p_{MenACWY-TT,X}$  excludes 0.30.

Confidence Intervals will be calculated using the Miettinen-Nurminen method [1, 2].

**Reporting:** The number ( $n_{V,X}$ ) and proportion ( $p_{V,X}$ ) of participants with seroprotective response will be provided (by arm), along with point and 95% CI estimates of the difference in proportions ( $p_{NmCV-5,X} - p_{MenACWY-TT,X}$ ).

**Graphical display:** None

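### Serogroup X superiority: Protocol 9.2 tests a 30-point null but declares success at a 10% lower limit, while SAP 8.3.1 requires the limit to exclude 30%

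*Protocol*

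**What the plan says.** Protocol 9.2 names superiority of NmCV-5 for serogroup X as a secondary objective. It tests a null difference "equal or less than 30% (0.3) versus an alternative hypothesis of the difference in proportions of 30% or greater". The next sentence is the only decision rule given there for this objective. It speaks of non-inferiority and is met when the lower bound of the two-sided 95% interval for the "difference in proportion of participants with seroprotective response is at or above 10" per cent.

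Protocol 9.6 says only that superiority will be "based on the difference in proportions of participants with seroprotective response to serogroup X and its 95% CI", by the Miettinen-Nurminen method. It gives no threshold.

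SAP 8.3.1 does give one. Its rule opens "NmCV-5 will be deemed superior to MenACWY-TT for eliciting a seroprotective response to serogroup X, by at least 30%, if the lower limit of"; it goes on to name 0.30 as the value that this limit of the 95% interval must exclude.

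SAP 3.2 says that, where an analysis set is also defined in Protocol Section 9, "the definition provided here will supersede that of the protocol". That clause is confined to analysis sets.

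**The concern.** The Protocol paragraph contradicts itself. A lower limit at or above 10% rejects a difference of 10 points or less; it cannot by itself reject 30 points or less. It also contradicts the SAP. As the texts stand, a lower limit between 10% and 30% meets the Protocol rule and fails the SAP rule, and no passage ranks one rule above the other. Two smaller faults sit in the same paragraph: the rule is labelled non-inferiority although the objective is superiority, and the null and the alternative both include exactly 30%.

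Unblinded group results on the secondary endpoints go to WHO in reports by age group before the study ends (Protocol 9.6, SAP 3.1). If the threshold were chosen after those results were seen, the superiority claim would be open to challenge.

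**Working it through.** **Inputs.** 366 NmCV-5 and 183 MenACWY-TT evaluable infants per age group (Protocol 9.3). Two-sided 95% Miettinen-Nurminen interval (Protocol 9.6, SAP 8.3.1). Thresholds 0.10 (Protocol 9.2) and 0.30 (SAP 8.3.1). The serogroup X rate in the MenACWY-TT arm is not given, so 5% to 65% is assumed. The NmCV-5 rate is also assumed.

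**Formula.** The lower limit exceeds a threshold d when

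Z(d) = (x1/n1 − x2/n2 − d) / √{[q1(1−q1)/n1 + q2(1−q2)/n2] × N/(N−1)} > 1.96,

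where q1 and q2 are the maximum-likelihood rates constrained to q1 − q2 = d, and N = n1 + n2. The success probability is the sum of Bin(x1; 366, p1) × Bin(x2; 183, p2) over all outcomes with Z(d) > 1.96.

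**Check against the plan.** With d = −0.10 the same calculation gives 99.97% at 95%/95% and 97.50% at 90%/90%, as in Protocol Table 8.

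**Which null does each rule test?** The ranges are over control rates of 5% to 65%.

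| True difference | Success under the 10% rule |
|---|---|
| 30 points | 99.5% to >99.99% |
| 25 points | 92% to 99.8% |
| 20 points | 61% to 93% |
| 15 points | 20% to 44% |
| 10 points | 2.3% to 2.6% |

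The 10% rule holds the one-sided 2.5% level only at a true difference of 10 points. The 30% rule succeeds 2.3% to 2.6% of the time at 30 points, as a test of the stated null should.

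**How far apart are the rules in the data?** With 30/183 control responders (16.4%), the 10% rule needs 125/366 (34.2%), a difference of 17.8 points. The 30% rule needs 199/366 (54.4%), a difference of 38.0 points. For control rates of 5% to 30%, the smallest winning difference is 15.6 to 18.9 points under the 10% rule and 36.3 to 38.5 under the 30% rule.

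**When would the verdict change?** NmCV-5 is assumed at 90%.

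| Control X rate | 10% rule | 30% rule |
|---|---|---|
| 40% or less | ~100% | at least 99.8% |
| 45% | ~100% | 96% |
| 50% | ~100% | 70% |
| 55% | ~100% | 24% |
| 60% | 99.9% | 2.5% |

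A hand check of the 50% row: SE = √(0.9×0.1/366 + 0.5×0.5/183) = √(0.000246 + 0.001366) = 0.0402. For the 30% rule, (0.40 − 0.30)/0.0402 − 1.96 = 0.53, and Φ(0.53) = 70%. For the 10% rule, 0.30/0.0402 − 1.96 = 5.5, which is about 100%.

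With NmCV-5 at 95% and controls at 55%, the split is about 100% against 75%. With controls at 30% or less and NmCV-5 at 85% to 95%, both rules succeed in about 100%.

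**The case against.** **The 10% may be a lost minus sign.** The sentence refers back to a response defined above and uses the word non-inferiority. It could be the primary serogroup X rule (above −10%) repeated with the sign dropped. The next paragraph, on the EPI vaccines, has similar sign slips. This reading cannot be excluded. On it, there is no rival 10% superiority rule, and a lower limit between 10% and 30% would not count as a Protocol success. But the Protocol would then misstate the primary rule and have no decision rule at all for its superiority test. The paragraph needs correcting either way.

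**The SAP governs in practice.** SAP 3.1 says that version 1.0 is finalized before the WHO-report analyses and that later changes are reported as post hoc. That makes 0.30 the rule the analysts would apply, and a switch to 10% would have to be disclosed. It still does not rank the SAP above Protocol 9.2, and SAP 8.3.1 does not acknowledge a departure from the Protocol.

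**Both rules will probably pass.** This largely stands. The comparator is described as "containing meningococcal serogroups A, C, W, and Y polysaccharides conjugated to TT", with no X component, so low control positivity is plausible. The only control figure for X in the documents is 16.2% (95% CI 8.7 to 26.6; Protocol Table 2). It is for a different vaccine and for seroresponse, not titres of 8 or more, so it is only suggestive. High background positivity is not shown, but it is not ruled out.

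**Conclusion.** The concern holds. Protocol 9.2 pairs a 30-point null with a 10% decision limit and the wrong label, and it disagrees with SAP 8.3.1. The Protocol null and the SAP agree on 30%; the 10% sentence is the one that does not fit. That the 10% rule fails to control error for the stated null follows from the wording alone; its size rests on the Protocol's evaluable numbers and the assumed control rates.

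The practical effect depends on a control rate that the documents do not state. With NmCV-5 at 90%, the rules start to part at about 45% control positivity and differ clearly from 50%. The co-primary non-inferiority claim is not affected. This should be fixed because it is the success rule for a formal secondary claim, but it does not threaten the trial.

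**What to change.** Before the unblinded analysis, rewrite the decision sentence in Protocol 9.2 so that superiority for serogroup X is declared only if the lower bound of the two-sided 95% interval is above 30% (0.30). Remove the reference to non-inferiority there, and state the alternative as a difference strictly greater than 30%.

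If the Protocol is not to be amended for this alone, add one sentence to SAP 8.3.1 saying that its 0.30 rule governs this objective in place of the 10% sentence in Protocol 9.2.

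The first route is a wording amendment, and under Protocol 8.1 "Any amendments to the protocol or consent materials will be approved by the IRB/IEC before they are implemented". The second costs one SAP sentence. Neither changes the SAP analysis or the sample size; Protocol Tables 8 and 9 do not power this objective.

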9.3 Sample Size Considerations

Table 8 shows power to test the non-inferiority of the seroprotective response to each of the serogroups A, C, W and Y elicited by the NmCV-5 vaccine, relative to the seroprotective response elicited by the MenACWY-TT vaccine, when administered as a single dose at either 9 months of age or 15 months of age. These calculations assume a non-inferiority margin of -10% (-0.1) for a one-sided hypothesis test, with a 2.5% Type I error rate, and using the Miettinen-Nurminen method for estimation of the 95% CI for the difference in proportions. The resulting power correspond to the sample size of at least 183 and 366 evaluable participants in each of the MenACWY-TT and NmCV-5 arms, respectively, where this target sample size results from the following assumptions:

- At least 600 enrolled participants will be randomly assigned to receive the study vaccine at 9 months of age and
- Among those randomized to receive the study vaccine at 15 months of age, at least 600 participants will receive it at the scheduled visit.
- For each vaccination age, participants will be randomly assigned, in a 1:2 ratio, to receive the MenACWY-TT or the NmCV-5 vaccine.

- At least 92.5% of the 600 enrolled and vaccinated participants will be followed up and contribute a sample for assessment at their Day 29 visit.

Finally, calculation of Power in Table 8 is based on assumed proportions of seroprotective response in the MenACWY-TT arms that are consistent with, if somewhat more conservative than, to those reported in the literature.

Table 8. Power to test non-inferiority of the proportion of participant with seroprotective response at Day 29 for serogroup A, C, W and Y, for a non-inferiority margin of -10% (-0.1) and a sample size of at least 183 and 366 evaluable participants in MenACWY-TT and NmCV-5 arms, respectively.

Serogroup	Proportion of Sero-response in MenACWY-TT arm	Difference in proportion of sero-response (NmCV-5 – MenACWY-TT)		Power
		Under the Null (H0)	Under the Alternative (H1)	
A	0.95	-0.1	0	99.97%
C	0.95	-0.1	0	99.97%
W	0.90	-0.1	0	97.50%
Y	0.90	-0.1	0	97.50%

Power calculations were performed computationally, based on the exact distribution of the primary endpoint of interest under the alternative hypothesis. The probability of each combination of outcomes in the active and control arms was obtained under the assumption that they follow independent binomial distributions. The power of the test was calculated as the sum of probabilities of those scenarios where the outcomes meet the non-inferiority criterion. A simulation was also conducted to corroborate the results.

Table 9 shows power to test the non-inferiority of the seroprotective response to serogroup X. Unlike serogroups A, C, W and Y, non-inferiority of the vaccine for serogroup X will be based on the difference in the proportion of participants randomized to receive NmCV-5 with seroprotective response to serogroup X minus the proportion of participants randomized to receive MenACWY-TT with seroprotective response to the serogroup with the lowest proportion of seroprotective response. Thus, for this test, and consistent with our assumptions listed above, we assume that the lowest proportion of seroprotective response in the MenACWY-TT will be 90% or higher.

Table 9. Power to test non-inferiority of the proportion of participant with seroprotective response at Day 29 for serogroup X, when compared to lowest seroprotective response rate among A, C, W, Y serogroups, with a non-inferiority margin of -10% (-0.1) and a sample size of at least 183 and 366 evaluable participants in MenACWY-TT and NmCV-5 arms, respectively.

Serogroup	Lowest Proportion of Sero-response among Serogroups A, C, W,	Difference in sero-response (Serogroup X in NmCV-5 - lowest proportion among Serogroups A, C, W, Y in MenACWY-TT)	Power
-----------	--	---	-------

	Y in MenACWY-TT arm	Under the Null (H0)	Under the Alternative (H1)	
X	0.90	-0.1	0	97.50%

Under the assumption that the test statistics used for the five non-inferiority tests described above are independent, the power to declare overall non-inferiority of NmCV-5 relative to MenACWY-TT at a given vaccination age is calculated to be at least 92.6%. We note, however, that this is a conservative assumption and, given the likely correlation between seroprotective response rates among all the serogroups, the overall power may be higher.

